## I. BACKGROUND AND RATIONALE

Over the past several years botulinum toxin type A (BTX-A, BOTOX®) has been used in many applications to prevent scar formation. Gassner and Sherris previously found that chemoimmobilization of facial wounds with BTX-A improved wound healing and cosmetic appearance. These clinical findings are supported by a randomized, double-blinded, placebo-controlled study showing a significant improvement in scar appearance in BTX-A treated facial wounds compared to saline injected controls. In addition, we recently published the first article demonstrating that BTX-A is effective in treating urethral strictures, which are caused by scar formation. Finally, Comperat and colleagues demonstrated that BTX-A injections in the bladder leads to less fibrosis. In the study, bladder wall specimens were obtained from cystectomy in 45 patients with neurogenic overactive bladders with and without injection of botulinum toxin A into the detrusor. Bladder wall specimens were evaluated for inflammation, edema, and fibrosis. When comparing specimen from patients who had received botulinum toxin injection to those from patients who had not, there was no difference concerning inflammation and edema. However, patients who had received botulinum toxin injection showed significantly less fibrosis of the bladder wall than those who had not received the toxin injection ( $p < 0.00073$ ).

A major contributor to fibrosis and scar formation is thought to be tension from the underlying muscle contractions acting on the wound edges during healing. BTX-A acts at the neuromuscular junction by blocking vesicle transport of acetylcholine, in essence producing a chemical denervation. By decreasing underlying muscle tension/spasm in healing wounds BTX-A may be a viable option to prevent fibrosis and scar formation.

Penile curvature secondary to scar or plaque formation along the shaft of the penis is known as Peyronie's disease. Significant penile curvatures can result in pain, poor erections, and an inability to engage in sexual intercourse. Peyronie's disease is an acquired disease of the tunica albuginea surrounding the corpora cavernosa of the penis and affects approximately 3% of the male population. The average age of onset of this disease is 57 years old. The etiology of Peyronie's disease remains unknown. However, many believe that traumatic inflammatory changes to the septal fibers of the erect penis from either blunt penile injury or repeated microtrauma associated with sexual activity.

Traditionally, treatments for Peyronie's disease have been limited and often unsuccessful. Oral medical therapies that prevent the scar formation and promote scar breakdown have been ineffective. Many patients with Peyronie's disease will require injection therapy of the penis. Injections of pharmaceutical agents directly into the Peyronie's plaque have been used for over 50 years in the treatment of clinically significant Peyronie's disease. The three most common agents used for injection therapy are verapamil, interferon, and collagenase. Intracellular calcium levels play an important role in the metabolism and synthesis of collagen. Calcium channel blockers such as verapamil increase collagenase activity and decrease collagen secretion, although quite high tissue doses are needed for this. Interferons are low molecular weight proteins involved in the normal function of the body's immune system. They are known to inhibit the proliferation of myofibroblasts, decrease collagen production, and increase the activity of collagenase. Finally, collagenase is a purified bacterial enzyme that attacks and

breaks down collagen. It has been used clinically to treat severe burns and lumbar disk disease. All three of the agents have been shown to result in mild to moderate improvement in penile curvature when compared to placebo.

There are two phases of Peyronie's disease: the active phase and the quiescent phase. The active phase usually occurs during the first 12 months of the disease and is associated with constant changing of the plaque and penile pain. Surgery is contraindicated during the active phase and is usually indicated after 18 months from the onset of the disease, when the plaque has stabilized. The stabilization of the plaque is known as the quiescent phase. During the active phase, approximately 15-20% of patients can get spontaneous resolution of their disease. Therefore, injections initiated during the active phase are also discouraged by some because this may lead to further trauma as opposed to allowing for spontaneous resolution.

*Hypothesis:* BTX-A penile injections into Peyronie's plaques can significantly prevent scar formation and promote scar breakdown as evidenced by reduced penile curvature.

## **II. PURPOSE**

The purpose of this study is to establish the efficacy of botulinum toxin in treating Peyronie's disease.

## **III. DRUG INFORMATION**

BOTOX® is the brand name for Botulinum toxin type A. For this study's treatment injections, we will be using 100 units of BOTOX® in 10 cc of preservative free normal saline, or 10 cc of preservative free normal saline for placebo.

BOTOX® and Placebo will be provided by Allergan, Inc.

BOTOX® is a purified neurotoxin complex supplied as a sterile, vacuum dried purified botulinum toxin type A, produced from fermentation of Clostridium botulinum type A.

One unit of BOTOX® corresponds to the calculated median intraperitoneal lethal dose (LD 50) in mice. The specific activity of BOTOX® is approximately 20 units/nanogram of neurotoxin protein complex.

BOTOX® blocks neuromuscular transmission by binding to acceptor sites on motor or sympathetic nerve terminals, entering the nerve terminals, and inhibiting the release of acetylcholine. This inhibition occurs as the neurotoxin cleaves SNAP-25, a protein integral to the successful docking and release of acetylcholine from vesicles situated within nerve endings. When injected intramuscularly at therapeutic doses, BOTOX® produces partial chemical denervation of the muscle resulting in a localized reduction in muscle activity. In addition, the muscle may atrophy, axonal sprouting may occur, and extra-junctional acetylcholine receptors

may develop. There is evidence that reinnervation of the muscle may occur, thus slowly reversing muscle denervation produced by BOTOX®.

BOTOX® is not expected to be present in the peripheral blood at measurable levels following IM or intradermal injection at the recommended doses. The recommended doses of neurotoxin administered at each treatment session are not expected to result in systemic, overt distant clinical effects, i.e., muscle weakness, in patients without other neuromuscular dysfunction. However, some clinical systemic effects have been shown by a single fiber electromyography after IM doses of botulinum toxins appropriate to produce clinically observable local muscle weakness.

BOTOX® is contraindicated in the presence of infection at the proposed injection site(s), and in individuals with known hypersensitivity to any ingredient in the formulation.

BOTOX® is supplied in a single-use vial. Each vial contains 100 units of vacuum-dried Clostridium botulinum type A neurotoxin components.

Unopened vials of BOTOX® should be stored in a refrigerator (2° to 8° C) for up to 24 months (or the expiration date on the product label). Administer BOTOX® within four hours of reconstitution and within 30 minutes of drawing into syringe; during this period the reconstituted BOTOX® should be stored in a refrigerator (2° to 8° C).

Additional BOTOX® information is available in the BOTOX® Prescribing Information package insert.

#### **IV. ELIGIBILITY CRITERIA**

##### **A. Inclusion:**

1. Subjects with stable Peyronie's plaques.
2. Males at least 18 years of age
3. Prior history of failed penile injection therapies is allowed.
4. Must give informed consent.

##### **B. Exclusion:**

1. Subjects in the active phase of Peyronie's disease.
2. Subjects with less than 1 year history of Peyronie's disease.
3. Subjects taking oral medications for Peyronie's disease which include Trentol, Viagra, vitamin E, colchicines, L-arginine, and tamoxifen. There will be a 2 week wash-out period if patients are on these medications.
4. Subjects with more than 1 penile plaque will be excluded from the study.
5. Subjects with calcified plaques demonstrated by ultrasound will be excluded from the study.
6. Known allergy or sensitivity to any components of the study medication (botulinum toxin A), anesthetics, or any other product associated with the treatment and general study procedures.

7. Any medical condition or neuromuscular disorder that may put the patient at increased risk with exposure to botulinum toxin A (BTX-A), including myasthenia gravis, Eaton-Lambert syndrome, or amyotrophic lateral sclerosis.
8. Patient taking aminoglycosides or any drug known to interfere with neuromuscular transmission.
9. Patient has hemophilia or other clotting factor deficiencies or disorders that cause bleeding diathesis.
10. Patient must not be taking aspirin, non-steroidal anti-inflammatory drugs, or Coumadin for 7 or more days prior to Botox injection.
11. Episode of unstable angina pectoris, myocardial infarction, transient ischemic attack, or cerebrovascular accident within the past 6 months.

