## V. DESIGN

This is a randomized, placebo-controlled, cross-over, single-center trial. Study drug is Botulinum toxin type A (BOTOX®). Subjects who meet the inclusion criteria for the study will be randomized to either the treatment or placebo arm.

**ARM 1 - Treatment:** Injection solution will consist of 100 units of BOTOX® in 10 cc of preservative free normal saline, or

**ARM 2 - Placebo:** Injection solution will consist of 10 cc preservative free normal saline.

The Week 16 Visit will be the end of the study participation for those subjects in Arm 1 and who did not develop ED (as defined as a drop in IIEF scores of more than 4 points from Baseline IIEF score). The Week 16 Visit will be the end of study participation for subjects in Arm 2 and who developed ED. For subjects in Arm 2, crossover to BOTOX treatment will begin after the Week 16 Visit by repeating the study schedule as for Week 0 to Week 16. Continuation visits at Months 6, 9, and 12 will occur for subjects in Arm 1 and who developed ED.

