## VI. RANDOMIZATION PROCEDURES:

The subjects will be randomized to the arms as they are enrolled and meet eligibility criteria. The odd number (1, 3, 5...) of subjects will be in ARM 1 and even numbers (2, 4, 6...) of subjects will be in the ARM 2. The randomization scheme will not result in selection bias.

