## VII. SCHEDULE OF EVENTS

PROCEDURE	Baseline (Pre-treatment)	Week 0 Clinic Visit	Week 2 Phone Visit	Week 4 Clinic Visit	Week 6 Phone Visit	Week 8 Clinic Visit	Week 10 Phone Visit	Week 12 Clinic Visit	Week 14 Phone Visit	 Week 16 Clinic Visit (  End of Study) (  Placebo Crossover)	 Month 6 Clinic Visit	 Month 9 Clinic Visit	 Month 12 Clinic Visit (End of Study)
Signed, written informed consent	X												
Medical history	X												
Physical examination	X									X	X	X	X
Blood pressure, pulse, O 2 saturation	X									X			
Penile injection: Caverject 20mcg/cc	X									X			
Penile curvature assessment & photos	X									X			
Penile ultrasound	X									X			
IIEF questionnaire	X									X			
Randomization	X												
Penile injection: BTX-A or  Placebo		X		X		X		X					
Collect AE information		X	X	X	X	X	X	X	X	X	X	X	X
Concomitant meds	X	X		X		X		X		X	X	X	X

End of study for subjects receiving BOTOX and did not develop ED (as defined as a drop in IIEF scores of more than 4 points from Baseline IIEF score).

End of study participation for subjects receiving placebo and develop ED.

For subjects receiving placebo, crossover to BOTOX treatment will begin by repeating the study schedule as for Week 0 to Week 16.

Continuation visits for subjects receiving BOTOX and developed ED.

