Subjects randomized to ARM 2 will receive one injection of 10cc preservative normal saline at Weeks 0, 4, 8 and 12.

All subjects will be telephoned two weeks after each injection to inquire on the occurrence of any adverse events. Subjects will be asked a general, non-direct question such as, "How have you been feeling since the last visit?" Direct questioning will then be done as appropriate.

At the completion of 16 weeks (4 weeks after last treatment), subjects will have a repeat penile injection of Caverject, penile pictures will be taken, and penile ultrasonography will be performed. Subjects will also be asked to complete the IIEF again.

The Week 16 Visit will be the end of the study participation for those subjects in Arm 1 and who did not develop ED (as defined as a drop in IIEF scores of more than 4 points from Baseline IIEF score). Subjects developing ED, will have continuation visits at Months 6, 9, and 12. At these visits, a complete physical will be done. Information about any adverse events and changes in concomitant medications will be collected. The subjects will complete the IIEF questionnaire.

If at the end of 16 weeks there is a significant improvement in the subjects treated with BTX-A as compared to the placebo arm, the men in the placebo arm will be given the option to cross over into the treatment arm and complete a 12 week course of BTX-A injections (1 saline injection, 1 Botox injection, 2 saline injections). For those in Arm 2 who develop ED, participation will end after the Week 16 visit.

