**Please circle your answer**

1. Over the past 4 weeks, how often were you able to get an erection during sexual activity?

No sexual activity .....	0
Almost never/never .....	1
A few times (much less than half of the time).....	2
Sometimes (about half of the time) .....	3
Most times (much more than half of the time).....	4
Almost always/always .....	5
  
2. Over the past 4 weeks when you had erections with sexual stimulation, how often were your erections hard enough for penetration?

No sexual activity .....	0
Almost never/never .....	1
A few times (much less than half of the time).....	2
Sometimes (about half of the time) .....	3
Most times (much more than half of the time).....	4
Almost always/always .....	5
  
3. Over the past 4 weeks when you attempted sexual intercourse, how often were you able to penetrate (enter) your partner?

Did not attempt intercourse .....	0
Almost never/never .....	1
A few times (much less than half of the time).....	2
Sometimes (about half of the time) .....	3
Most times (much more than half of the time).....	4
Almost always/always .....	5
  
4. Over the past 4 weeks during intercourse, how often were you able to maintain your erection after you had penetrated (entered) your partner?

Did not attempt intercourse .....	0
Almost never/never .....	1
A few times (much less than half of the time).....	2
Sometimes (about half of the time) .....	3
Most times (much more than half of the time).....	4
Almost always/always .....	5
  
5. Over the past four weeks, during sexual intercourse, how difficult was it to maintain your erection to completion of intercourse?

Did not attempt intercourse .....	0
Extremely difficult .....	1
Very difficult .....	2
Difficult .....	3
Slightly difficult .....	4
Not difficult .....	5
  
6. Over the past four weeks, how many times have you attempted sexual intercourse?

No attempts.....	0
One to two attempts .....	1
Three to four attempts.....	2
Five to six attempts .....	3
Seven to ten attempts .....	4
Eleven or more attempts .....	5
  
7. Over the past four weeks when you attempted sexual intercourse, how often was it satisfactory for you?

Did not attempt intercourse .....	0
Almost never/never .....	1
A few times (much less than half of the time).....	2
Sometimes (about half of the time) .....	3
Most times (much more than half of the time).....	4
Almost always/always .....	5

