## International Index of Erectile Function (IIEF) Questionnaire\*

8. Over the past four weeks, how much have you enjoyed sexual intercourse?

- No intercourse..... 0
- No enjoyment..... 1
- Not very enjoyable ..... 2
- Fairly enjoyable..... 3
- Highly enjoyable..... 4
- Very highly enjoyable ..... 5

9. Over the past four weeks, when you had sexual stimulation or intercourse, how often did you ejaculate?

- No sexual stimulation/intercourse ..... 0
- Almost never/never ..... 1
- A few times (much less than half of the time)..... 2
- Sometimes (about half of the time) ..... 3
- Most times (much more than half of the time) ..... 4
- Almost always/always ..... 5

10. Over the past four weeks when you had sexual stimulation or intercourse, how often did you have the feeling of orgasm or climax?

- No sexual stimulation/intercourse ..... 0
- Almost never/never ..... 1
- A few times (much less than half of the time)..... 2
- Sometimes (about half of the time) ..... 3
- Most times (much more than half of the time) ..... 4
- Almost always/always ..... 5

11. Over the past four weeks, how often have you felt sexual desire?

- Almost never/never ..... 1
- A few times (much less than half of the time)..... 2
- Sometimes (about half of the time) ..... 3
- Most times (much more than half of the time) ..... 4
- Almost always/always ..... 5

12. Over the past four weeks, how would you rate your level of sexual desire?

- Very low/none at all..... 1
- Low ..... 2
- Moderate ..... 3
- High..... 4
- Very high..... 5

13. Over the past four weeks, how satisfied have you been with your overall sex life?

- Very dissatisfied..... 1
- Moderately dissatisfied..... 2
- About equally satisfied and dissatisfied..... 3
- Moderately satisfied ..... 4
- Very satisfied ..... 5

14. Over the past four weeks, how satisfied have you been with your sexual relationship with your partner?

- Very dissatisfied..... 1
- Moderately dissatisfied..... 2
- About equally satisfied and dissatisfied..... 3
- Moderately satisfied ..... 4
- Very satisfied ..... 5

15. Over the past four weeks, how do you rate your confidence that you could get and keep an erection?

- Very low ..... 1
- Low ..... 2
- Moderate ..... 3
- High..... 4
- Very high..... 5

\*RC Rosen, A Riley, G Wagner et al. The international index of erectile dysfunction (IIEF): a multidimensional scale for assessment of erectile dysfunction. Urology 1997 49: 822-30.

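### The 2-week wash-out is shorter than the IIEF's 4-week recall and tied to no visit, so a recent Viagra user's Baseline IIEF, and the ED label built on it, can be partly or wholly on-drug

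*Combined protocol and SAP*

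**What the plan says.** Section IV.B item 3 excludes men taking oral drugs for Peyronie's disease, naming Viagra among them, and then qualifies this: "There will be a 2 week wash-out period if patients are on these medications". It does not say which visit the two weeks precede.

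The IIEF in Appendix I looks back four weeks in every item, from the first ("Over the past 4 weeks, how often were you able to get an erection during sexual activity") to the last ("Over the past four weeks, how do you rate your confidence that you could get and keep an erection").

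Section VII puts consent, the first IIEF and randomization in one Baseline column. It has no wash-out row and no earlier visit. Section VI adds: "The subjects will be randomized to the arms as they are enrolled and meet eligibility criteria". Section XVII.B requires consent before any protocol-related procedure.

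Section V defines ED as "a drop in IIEF scores of more than 4 points from Baseline IIEF score". In Arm 1 the label triggers visits at Months 6, 9 and 12. In Arm 2, Section V says "crossover to BOTOX treatment will begin after the Week 16 Visit by repeating the study schedule", but Section VIII makes crossover optional and conditional on a significant benefit, and adds: "For those in Arm 2 who develop ED, participation will end after the Week 16 visit". Section XII lists IIEF change as a secondary outcome.

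The Section VII row "Concomitant meds" is ticked at Baseline, at every clinic visit from Week 0 to Week 16, and at Months 6, 9 and 12. No section says how those entries bear on the ED label or the IIEF analysis, or whether the listed drugs may be used after entry.

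**The concern.** A wash-out is meant to stop a prior drug from influencing the measurement that follows. For a questionnaire with a four-week look-back, two weeks off drug cannot do that. If Viagra raises IIEF scores while it is in use, a man who stopped recently gives a Baseline that is too high for his off-drug state.

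That Baseline is the fixed reference for a rule applied to each man individually, and the error can go either way:

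- **He stays off Viagra to Week 16.** Part of his fall is only the loss of the drug, and ED can be over-called.
- **He resumes before Week 16.** His Week 16 recall can contain more on-drug time than his Baseline recall did, and a true fall can be masked.

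The label has consequences for the man. In Arm 1 it decides whether he is followed to Month 12. In Arm 2 it ends participation and any chance of crossover. It also feeds the description of a risk that Section IX calls unknown.

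**Working it through.** **Inputs from the documents.** Wash-out 2 weeks (IV.B item 3). Recall 4 weeks (Appendix I). ED threshold a fall of more than 4 points, so at least 5 on whole-number scores (V). Arms of 10 (XI).

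**Inputs not in the documents, assumed here.** Viagra's benefit on the score: 2 to 8 points. SD of the change from Baseline to Week 16: 5, range 4 to 8. Change is taken as normal and the benefit as averaged evenly over the recall period. The plan states no figure of its own to reproduce.

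**Step 1: on-drug share of the Baseline recall.** With g drug-free weeks before the Baseline IIEF, share = max(0, 4 − g)/4.

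| Drug-free weeks g | 0 | 1 | 2 | 3 | 4 |
|---|---|---|---|---|---|
| On-drug share | 100% | 75% | 50% | 25% | 0% |

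A wash-out just completed at Baseline gives g = 2 and 50% (14 of 28 days). A wash-out that starts at Baseline and ends by Week 0 gives g = 0 and 100%. This step needs no assumption beyond when the wash-out falls.

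**Step 2: inflation of Baseline.** Inflation = share × benefit. At 50% it is 1 to 4 points, and at 100% it is 2 to 8 points, against the 5 needed for the label. With no true change and no noise, a benefit above 8 points is needed to trigger the label at 50% (0.5 × 8 = 4, which is not more than 4). A benefit of 5 is enough at 100%.

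**Step 3: over-calling (illustration).** For a man off drug to Week 16 with no true change, P(label) = Φ((share × benefit − 4.5)/SD). Ranges run over benefit 2 to 8.

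| Share | SD 4 | SD 5 | SD 8 |
|---|---|---|---|
| 0% | 13% | 18% | 29% |
| 25% | 16%–27% | 21%–31% | 31%–38% |
| 50% | 19%–45% | 24%–46% | 33%–48% |
| 100% | 27%–81% | 31%–76% | 38%–67% |

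At SD 5 and 50% share, each affected man adds 0.242 − 0.184 = 0.06 to 0.460 − 0.184 = 0.28 expected false labels. Noise alone at SD 5 would label 20 × 0.184 = 3.7 of 20 men, and no wash-out rule changes that.

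**Step 4: masking (illustration).** For a man with a true fall of 6 points who has fully resumed before the Week 16 window, observed fall = 6 − (1 − share) × benefit, and P(label) = Φ((observed fall − 4.5)/5).

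| Baseline share | P(label), benefit 2 to 8 |
|---|---|
| 100% (both windows fully on-drug) | 62% |
| 50% | 54%–31% |
| 0% (4-week wash-out) | 46%–10% |

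So a longer wash-out on its own makes masking worse in men who resume. The two recall windows have to be in the same drug state.

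**Step 5: secondary IIEF comparison.** At 50% share, one extra recent user in an arm of 10 shifts the mean difference by 0.5 × (2 to 8)/10 = 0.1 to 0.4 points. At 100% share the shift is 0.2 to 0.8. The standard error at SD 5 is 5 × √(2/10) = 2.2.

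**The case against.** The strongest reply is that the consequence is small and its size unknown. Exclusion 3 covers drugs taken for Peyronie's disease, and nothing says how many of the 20 men would be recent Viagra users. It may be none. The protocol does not say whether its IIEF threshold refers to the total or a domain score, so an assumed benefit of 2 to 8 points and an SD of 5 cannot be judged against it. The desire and relationship items need not respond to Viagra at all. A false label in Arm 1 adds three follow-up visits, which errs on the cautious side. In Arm 2 it costs a crossover that is already optional and conditional. All of this stands, and it is why the point is minor.

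Four stronger readings are tempting, and the documents do not support them:

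- **That 50% is the documented maximum, or that 100% is what the plan prescribes.** Randomization on meeting eligibility, in the Baseline column, suggests a wash-out complete by Baseline. Consent in that same column suggests one that starts there. The text settles neither.
- **That Viagra is allowed during the study.** The protocol is silent. Exclusion 3 may be meant to continue, and Appendix II (4.1.2.2) makes use of an unpermitted agent a major deviation.
- **That ED detection rests on this label alone.** Adverse events are collected at every visit and call from Week 0, with direct questioning as appropriate, so erectile problems can surface there.
- **That the arms are compared unfairly.** Both face the same rule, so a shift arises only if recent users happen to be unevenly split.

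Recording concomitant medications answers the concern only in part. The data would largely exist, but no rule uses them.

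**Conclusion.** The mismatch is real: a 2-week wash-out, not anchored to a visit, against a 4-week recall. The on-drug share of a recent user's Baseline recall is 50% if the wash-out is complete by the Baseline IIEF, and up to 100% if it runs between Baseline and Week 0. Given that Viagra raises IIEF scores while in use, which is an assumption here, his ED label can be wrong in either direction. His secondary IIEF change is also affected.

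The limits are equally clear. The primary outcome, curvature measured from photographs, does not depend on recall. No systematic between-arm bias follows. The mislabelling probabilities show what assumed benefits and SDs would imply for one affected man. They are not estimates for this trial. Severity is minor: a cheap improvement to how ED is labelled.

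**What to change.** 1. In IV.B item 3, require at least 4 weeks off Viagra, completed before the Baseline IIEF. Show this in the Section VII schedule and record the date of last use. The Baseline on-drug share becomes (4 − 4)/4 = 0% for a man who complies.
2. State that exclusion 3 continues through the Week 16 IIEF. This must accompany item 1, because a longer wash-out alone worsens masking in men who resume.
3. Where use occurs anyway, report ED and IIEF change with and without men whose Baseline or Week 16 recall window includes use. The Week 12 and Week 16 medication entries already bracket the later window. This report shows how far the results depend on such men; it does not correct an individual's label.

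Cost: protocol wording, one schedule line and one date field. Users of these drugs would wait about 2 more weeks before Week 0 and would abstain to Week 16, and a few recruits may be lost.
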